### 4.2.2 Efficacy endpoints

#### 4.2.2.1 Primary endpoint

Percent change from baseline in NRS to week 4 (weekly average of the peak).

#### 4.2.2.2 Secondary efficacy endpoints

- Absolute and percent change from baseline in weekly average of the peak and average pruritus NRS to each visit
- Absolute and percent change from baseline in weekly average of the peak and average VRS to each visit
- DPS at hours 24, 48, and 72 for baseline and Week 4 visits
- Absolute change from baseline in PAS Item 5 (number of lesions) to each visit

- PAS Item 6 (excoriation/crusts and healed lesions stages) at each visit
- IGA at each visit
- Proportion of subjects achieving IGA success (defined as IGA=0[clear] or IGA=1[Almost clear] with two-point improvement from baseline) at Week 12

#### 4.2.2.3 Other efficacy endpoints

- Absolute change and shift from baseline in Dermatology Life Quality Index (DLQI) to each visitAbsolute and percent change from baseline in weekly average Sleep Disturbance Numeric Rating scale (NRS) up to Week 4
- Objective assessment of scratching events during the night and sleep duration using Actigraphy. Ratio 'scratching duration/duration' and 'scratching events/duration' up to week 4 are the study endpoints.

### 4.2.3 Safety Variables

Safety assessments will be conducted for all subjects at the screening visit (upon the signature of the informed consent form [ICF]) and at every subsequent visit.

Safety assessments include electrocardiogram (ECG), physical examination, vital signs, body weight, respiratory assessments (peak expiratory flow [PEF] measurement only for subjects with a medical history of asthma), laboratory safety tests, and AE recording (including serious AEs [SAE] and AEs of Special Interest [AESI]).

#### 4.2.3.1 Electrocardiograms (ECG)

A 12-lead ECG will be performed at screening 1, baseline and Week 8, or early termination and/or unscheduled visits when applicable.

All abnormal ECG findings considered to be clinically significant by the investigator at the screening visit will be recorded in the Medical History form. Any clinically significant changes from the screening visit will be reported as AEs in the eCRF.

#### 4.2.3.2 Physical examination and vital signs

**Physical examination:** The physical examination will be performed at screening 1, baseline, weeks 4, 8, 12, 18, or early termination and/or unscheduled visits when applicable.

All clinically significant abnormal findings at the screening visit will be recorded in the Medical History form. Any clinically significant changes from the screening visit will be recorded as an AE.

**Vital signs:** The vital signs will be evaluated at screening 1, baseline, weeks 1, 2, 4, 8, 12, 16, 18, or early termination and/or unscheduled visits when applicable.

Vital signs will include pulse rate, systolic and diastolic blood pressure (after the subject has been sitting for at least 5 minutes). All abnormal values at the screening visit identified as clinically significant by the investigator will be recorded in the Medical History form. Any clinically significant changes from the screening visit will be recorded as an AE.

**Height and Weight:** Height will be measured at the baseline visit only, and weight will be measured at baseline, weeks 4, 8, and 12.

Any clinically significant weight changes from the screening visit will be recorded as an AE.

Blood pressure (systolic and diastolic), pulse rate, and weight values meeting criteria for potentially clinically significant values (PCSV) will be reported.

Criteria for PCSV for vital signs and weight are listed in Appendix 2.

#### 4.2.3.3 Respiratory Assessments

At each visit, investigator or designee will perform a respiratory physical examination and ask all subjects whether they have experienced any signs/symptoms of asthma. In addition, for subjects reporting a medical history of asthma, PEF will be performed. PEF measurements should consist of 3 good efforts, with the best result documented.

Newly diagnosed asthma or worsening of asthma during the study will be reported as AESI.

#### 4.2.3.4 Laboratory safety tests

The following laboratory safety tests will be performed:

TP-GDO-WW-016-07  
Effective Date: 05 Sep 2018  
Related to: SOP-GDO-WW-019

CONFIDENTIAL

Project Document Version No. 2.0  
Project Document Effective Date: Date of last signature  
Page 18 of 59

- Hematology: white blood cell (WBC) count with differential count (including eosinophils), red blood cell (RBC) count, hemoglobin (Hb), hematocrit (hct), mean cell volume (MCV), and platelet count (Plt)
- Blood chemistry: sodium, potassium, calcium, chloride, glucose, urea, creatinine, aspartate aminotransferase (AST)/ alanine aminotransferase (ALT), alkaline phosphatase (ALP), total and direct bilirubin, creatinine phosphokinase (CPK), high sensitivity C-reactive protein (hsCRP), fibrinogen, gamma-glutamyl transpeptidase (GGT), lactate dehydrogenase (LDH), total protein, albumin, uric acid, total cholesterol, low-density lipoprotein (LDL), high-density lipoprotein (HDL) and triglycerides
- CPK isoenzyme test will be performed only if CPK is elevated to >2.5X Upper Limit of Normal (ULN).
- Urinalysis: blood, proteins, leukocytes, glucose, ketones, nitrites, bilirubin, urobilinogen, pH, and specific gravity

All clinically significant out-of-range laboratory values at the screening visit will be recorded in the medical history form. All clinically significant out-of-range laboratory values after the screening visit are to be reported as an AE if this abnormality was not present at the screening visit or is assessed as having worsened since the screening visit (i.e., changed significantly from the screening visit).

#### 4.2.3.5 Adverse events

Adverse events (AE) will be coded using the Medical Dictionary for Regulatory Activities (MedDRA) version 19.0.

An AE will be considered a treatment-emergent AE (TEAE) if it started after the date of the first dose of study drug or it started before the date of the first dose of study drug and worsened after the date of the first dose. AEs occurring on the date of the first dose of study drug will be considered a TEAE if the onset of the AE is on or after the time of injection on that day. Where dates are missing or partially missing, AEs will be assumed to be treatment-emergent, unless there is clear evidence (through comparison of partial dates) to suggest that the AE started prior to the first dose of study treatment.

The investigator will have to assess if there is a reasonable possibility of a causal relationship between the study drug and/or a study procedure (e.g. injection, blood sample collection) and an AE. Related AEs will be defined as study drug related AEs or study procedure related AEs.

The AESIs for this clinical trial have been defined as follows:

- Elevated ALT or AST ( $> 3$  ULN) in combination with elevated bilirubin  $> 2$  ULN, whether or not considered as related to the study drug by the investigator
- Elevated CPK ( $\geq 2.5$  ULN), if considered as related to the study drug by the investigator
- Asthma or worsening of asthma
- IRR (local and systemic reactions, including hypersensitivity)
- Peripheral edema
- Skin or systemic infection
- Headache
- Exacerbation of AD, in subjects with medical history of AD

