7.2.4.1 Definitions

7.2.4.1.1 *Adverse events (AE)*

According to ICH E2A, an AE is any untoward medical occurrence in a subject or clinical investigation subject administered a pharmaceutical product and which does not necessarily have a causal relationship with this treatment. An AE can therefore be any unfavorable and unintended sign (including an abnormal laboratory value), symptom, or disease temporally associated with the use of a medicinal (investigational) product, whether or not related to the medicinal (investigational) product.

Thus any new sign, symptom or disease, or any clinically significant worsening of an existing sign, symptom or disease compared to the condition at the first visit (including disease treated), should be considered as an AE. Lack of efficacy is not considered as an AE.

Notes:

- Any new sign or symptom reported by the subject that appears after accidental or intentional overdose or misuse should also be reported as an AE.
- There should be an attempt to report a diagnosis rather than the signs, symptoms or abnormal laboratory values associated with the report of an AE. However, a diagnosis should be reported only if, in the Investigator's judgment, it is relatively certain. Otherwise, symptoms, signs, or laboratory values should be used to describe the AE.
- Pregnancy is not to be considered as an AE; however, is an important medical event that must be monitored as described in Section 7.2.4.2.4.
- Each new episode of a chronic disease (e.g. hay fever, allergy, etc.) from the screening visit should be reported as a new AE.

7.2.4.1.2 *Serious Adverse events (SAE)*

A SAE is any untoward medical occurrence that meets any of the following criteria :

- Results in death,
- Is life-threatening,
- Requires inpatient hospitalization or prolongation of existing hospitalization,

- Results in persistent or significant disability/incapacity, or
- Is a congenital anomaly/birth defect.

Important medical events that may not result in death, be life-threatening, or require hospitalization may be considered a SAE when, based upon appropriate medical judgment, they may jeopardize the safety of the subject, and may require medical or surgical intervention to prevent one of the outcomes listed in this definition. Examples of such events are intensive treatment in an emergency room or at home for allergic bronchospasm, blood dyscrasias, or convulsions that do not result in hospitalization.

Note:

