- Between the study drug (nemolizumab or its placebo) and the AE, and/or
- Between a clinical trial protocol procedure (e.g. injection, blood sample collection) and the AE

No Reasonable Possibility:

No suggestive evidence or arguments can be identified regarding a causal relationship between the study drug or a clinical trial protocol procedure and the AE.

7.2.4.2 *Reporting procedures*

7.2.4.2.1 *Procedures for reporting Adverse Events*

The collection of AEs is from the time that a subject signs the ICF to their final visit.

At each post-enrolment visit, the Investigator (or sub-Investigator) will question the subject about AEs using an open non-persuasive question to elicit reporting of AEs, for example “Have you noticed any change in your health since the last visit?” Directed questioning and examination will then be performed as appropriate.

Any AE occurring during the AE reporting period, whether it is related to the study drug(s) and/or study procedure(s) or not, will be recorded immediately in the source document, and described on the Adverse Event Form of the eCRF along with the date of onset, severity, relationship to the study drug(s) and/or study procedure(s), and outcome, without omitting any requested and known information. Additional information will be requested under certain circumstances (e.g. for AESI).

Adverse Events (AEs) assessed as related to the treatment or study procedure will be monitored until they have resolved or reached a stable condition. Other AEs will be monitored until the last visit if they have not resolved or reached a stable condition.

Reporting procedures for SAEs (see Section 7.2.4.2.2), AESI to be reported within 24 hours (see Section 7.2.4.2.3), and pregnancies (see Section 7.2.4.2.4) must be followed.

7.2.4.2.2 *Procedure for reporting a Serious Adverse Event*

For a SAE occurring during the clinical trial, regardless of whether it is related to the study drug and/or study procedure or not, the Investigator must :

1. Take prompt and appropriate medical action, if necessary. The safety of the subject is the first priority.

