10. Provide the subject with the watches for Actigraphy assessments
11. Schedule the Visit 3/Day 1.

8.1.2 *Treatment period*

8.1.2.1 *Visit 3 / Baseline visit (Day 1)*

At the Baseline visit, the Investigator or designee will:

1. Ask the subject about AEs using an open-ended question, such as "Have you noticed any change in your health since the last visit?" Record all events, as appropriate, on the corresponding eCRF form(s).
2. Check laboratory results (hematology, biochemistry, virology, urinalysis, IgE, TB tests) from the Screening visits.

3. Complete urine pregnancy test if the subject is a female of childbearing potential.
4. Ask the subject about any changes in his/her concomitant therapies/procedures (added, removed or changed) since the previous visit. Record all changes in the source document and the eCRF.
5. Perform a physical examination (including height and weight), vital signs measurements and ECG.
6. Conduct respiratory medical assessments, including PEF for subjects with a history of asthma
7. Check subject's record for pruritus NRS and VRS and sleep disturbance NRS.
8. Confirm the eligibility of the subject according to inclusion and exclusion criteria. Enroll the subject in the clinical trial and record the corresponding SIN in the eCRF
9. Complete the evaluation of PAS and IGA.
10. Take whole body photographs (selected centers only).
11. Ask subject to complete the DLQI.
12. Check subject's use of watches for Actigraphy
13. Collect urine for urinalysis.
14. Collect blood sample for hematology, and entire blood biochemistry
15. Perform D-Squames.
16. Perform 4-mm biopsies for subjects who consented by signing the additional ICF
17. Collect blood samples for PK, ADA & biomarkers before drug injection.
18. The pharmacist (or other qualified personnel) will:
 - a. Prepare the syringe of dosing solution of appropriate volume of nemolizumab or placebo according to the pharmacy manual and the specific instruction provided by the IRT system;
 - b. Provide the prefilled syringe to the blinded investigator or qualified personnel for injection.
19. Blinded investigator or qualified personnel will administer the study drug subcutaneously to the subject, who will remain under medical observation for at least 30 minutes before been discharged.

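### As worded, the TEAE rule misses some AEs that begin before the first injection and worsen after it: worsening only on the first-dose date, or onset on that date before the injection

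*SAP*

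**What the plan says.** SAP 4.2.3.5 (Adverse events) gives three routes to treatment-emergent status.

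- **Route A:** onset on a date later than the first-dose date.
- **Route B:** "it started before the date of the first dose of study drug and worsened after the date of the first dose". This is the only route that mentions worsening.
- **Route C:** an AE occurring on the first-dose date "will be considered a TEAE if the onset of the AE is on or after the time of injection on that day".

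A default follows: "Where dates are missing or partially missing, AEs will be assumed to be treatment-emergent", unless the partial dates clearly point to a start before dosing.

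AEs are collected well before dosing. Protocol 7.2.4.2.1 states: "The collection of AEs is from the time that a subject signs the ICF to their final visit". The same section says that each AE is described "along with the date of onset, severity, relationship to the study drug(s) and/or study procedure(s), and outcome"; a date of worsening is not in that list.

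Two provisions bear on whether worsening gets its own record. Protocol 7.2.4.1.1 includes among AEs "any clinically significant worsening of an existing sign, symptom or disease compared to the condition at the first visit". SAP 4.2.3.4 says: "All clinically significant out-of-range laboratory values after the screening visit are to be reported as an AE", provided the abnormality is new or worse than at screening. Protocol 7.2.3 has the same laboratory rule.

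**The concern.** A treatment-emergent rule should separate what happened before exposure from what happened after it. Exposure begins at the injection, not at midnight, and Route C recognises this for onset. Nothing does the same for worsening.

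The Day 1 schedule makes the pre-injection hours a real source of AEs. In Protocol 8.1.2.1, step 14 is "Collect blood sample for hematology, and entire blood biochemistry", step 16 is the optional biopsies, and the injection is step 19. An abnormality found in the pre-dose sample, or a reaction to a pre-dose procedure, has an onset on the first-dose date before the injection. If it then gets worse, no route admits it.

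At stake is the content of the tables in SAP 5.8.2 and 5.8.3 that are restricted to TEAEs, severe TEAEs and serious TEAEs. The omission also runs against the SAP's own cautious approach. Missing dates default to treatment-emergent, missing severity becomes severe and missing relationship becomes related, yet a fully dated event that worsens after exposure is left out.

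**Working it through.** There is no planned figure to reproduce, because the point concerns a definition. The check applies Routes A, B and C literally, with all dates and times known and each AE held as one record. It compares the result with a dose-time rule: onset at or after the injection, or onset before it with worsening at or after it. D1 is the first-dose date; pre and post refer to the injection.

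| Onset | Worsening | SAP rule | Dose-time rule |
|---|---|---|---|
| Before D1 | None | No | No |
| Before D1 | Before D1 | No | No |
| Before D1 | D1 pre | No | No |
| **Before D1** | **D1 post** | **No** | **Yes** |
| Before D1 | After D1 | Yes | Yes |
| D1 pre | None | No | No |
| D1 pre | D1 pre | No | No |
| **D1 pre** | **D1 post** | **No** | **Yes** |
| **D1 pre** | **After D1** | **No** | **Yes** |
| D1 post | None | Yes | Yes |
| D1 post | D1 post | Yes | Yes |
| D1 post | After D1 | Yes | Yes |
| After D1 | None | Yes | Yes |
| After D1 | After D1 | Yes | Yes |

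The rules differ in 3 of 14 cells and agree in 11.

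**Case (a), onset before D1, worsening on D1 after the injection.** Route A fails because onset is not after the date. Route B fails because the worsening is on the date, not after it. Route C fails because onset is not on or after the injection. If the same AE worsens again after D1, Route B admits it. The case is therefore limited to AEs whose only post-dose worsening is on the injection day.

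**Case (b), onset on D1 before the injection, worsening at any later time.** Route A fails because onset is on the date, not after it. Route B fails because onset is on the date, not before it. Route C fails because onset precedes the injection. A worsening weeks later does not change the result.

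The missing-date default does not help, because in these cases the dates are known.

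**Illustration of case (b).** Suppose the pre-dose D1 sample shows a clinically significant CPK rise that was absent at screening, and the Week 4 sample (Protocol 8.1.2.3, step 11) shows a higher value. If the site keeps one record dated D1 before dosing, it is not a TEAE. If the site enters the Week 4 value as its own AE, Route A makes it one.

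**Where the events would still appear.** SAP 5.8.2 lists all AEs by subject, and SAP 5.8.3 lists deaths and other SAEs without a TEAE restriction. A laboratory change also remains in the shift and PCSV summaries of SAP 5.8.4. AESIs are less clear. The summary line in SAP 5.8.3 is not worded as TEAE-only, but the section opens by placing AESIs among other significant TEAEs, so that summary may be affected too.

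**The case against.** The strongest reply is that the protocol may turn worsening into a separate AE. An AE that arose after the first visit and then worsens is, by definition, worse than at that visit, so it meets the comparator in Protocol 7.2.4.1.1. The laboratory rule in SAP 4.2.3.4 and Protocol 7.2.3 can be read value by value, so a higher Week 4 CPK could qualify in its own right. The absence of a worsening date from the fields listed in Protocol 7.2.4.2.1 points the same way. A new record has its own onset, and Route A or C admits it.

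This narrows the gap but does not close it. No document says that further worsening of an AE already recorded must open a second record. The explicit new-record instruction in Protocol 7.2.4.1.1 concerns new episodes of chronic disease. Protocol 7.2.3 has clinically relevant values repeated and followed until normal or explained, which fits one continuing record. Route B itself assumes that worsening can sit under an earlier onset; if every worsening opened a new record, that route would be largely redundant.

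A second reply is that the practical effect depends on the eCRF, which is not among the documents. That is right. If worsening is not dated within a record, no worsening limb, present or proposed, can be applied reliably. Likewise, a fully dated Day 1 AE with no recorded time has no stated rule, but this matters only if the eCRF allows the time to be missing.

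A reader might infer that the safety tables are materially wrong or favour nemolizumab. The documents do not support that: the rule is the same in both arms and no count of affected events can be derived. Nor do they support a percentage of worsening missed, since the timing of onset and worsening would have to be invented.

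**Conclusion.** The point holds as a minor defect of wording. Read literally, SAP 4.2.3.5 misclassifies cases (a) and (b), and no other section corrects it. The conclusion rests on two conditions: dates and times are known, and the worsening is held under the earlier onset.

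The number of events cannot be derived and is probably small. For scale only, one subject in an arm of 35 is 1/35 = 2.9 percentage points in an incidence table; this is not an estimate of how often the gap would bite. No efficacy analysis uses the rule.

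It would be too strong to say that AEs ongoing at dosing are generally lost when they worsen. Those that began before the first-dose date and worsened on a later date are captured already.

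**What to change.** In SAP 4.2.3.5, replace the present rule with:

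> An AE is treatment-emergent if its onset is at or after the time of the first injection, or if its onset is before the first injection and it worsens at or after the first injection.

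This corrects the three differing cells and leaves the other 11 unchanged. The existing default for missing or partial dates can stay.

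If the eCRF allows a missing time, add:

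> If the time of onset or worsening on the date of the first dose is not recorded, it is taken to be after the injection unless the record clearly shows otherwise.

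The cost is one or two sentences. The present rule already relies on a dated worsening and on injection and onset times for Day 1; the only further item is a time for worsening on that day, which the optional sentence covers. The small downside is that a few untimed pre-injection Day 1 events may be counted as TEAEs, by the same rule in both arms. The sponsor should also check in the eCRF whether worsening is dated within a record. Under SAP 5.11 the change should be final before database lock.

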#### **Missing date information for AEs**

The following imputation rules only apply to cases in which the start date for AEs is incomplete (i.e., partial missing):

#### **Missing Month and Day**

- If the year of the incomplete start date is the same as the year of the first administration of the study drug, then the month and day of the first administration of the study drug will be assigned to the missing fields.
- If the year of the incomplete start date is before the year of the first administration of the study drug, *December 31* will be assigned to the missing fields.
- If the year of the incomplete start date is after the year of the first dose of double-blind IP, *January 1* will be assigned to the missing fields.

#### **Missing Month Only**

- If only the month is missing, then the day will be treated as missing and both the month and the day will be replaced according to the procedure above.

